## Protocol Template Form

Item 1 UTHSCSA Tracking Number	HSC20150859H
--------------------------------	--------------

Item 2 Abstract / Project Summary	Provide a succinct and accurate description of the proposed research. State the purpose/aims. Describe concisely the research design and methods for achieving the stated goals. This section should be understandable to all members of the IRB, scientific and non-scientific. DO NOT EXCEED THE SPACE PROVIDED.
-----------------------------------	--

**Purpose/Objectives:** Nausea is a common symptom encountered in the Emergency Medical Services (EMS) environment that is often treated with oral or intravenous anti-emetic medications. **Research Design/Plan:** This will be a randomized equivalence study comparing the reduction in a patient's reported level of nausea after treatment with either Ondansetron or Isopropyl Alcohol

**Methods:** Patients who report nausea and/or vomiting in the normal evaluation and care of after calling 911 for Emergency Medical Care will be offered enrollment in the study. A short script will be attached to the outside of each study packet providing information about the study and its risks and benefits. Verbal or written (waiver of informed consent will be requested) permission will be obtained to start randomization. If the patient agrees to enroll then the study packet will be opened and utilized. All Advanced Life Support Ambulances in the San Antonio Fire Department will have sealed numbered opaque boxes or envelopes with either: 70% Isopropyl Alcohol swabs or ondansetron. Six Visual Nausea Severity Scoring cards will be provided with a marking pen to record timed nausea levels before and upon arrival to the Emergency Department and 15 minutes after treatment whichever comes first.

**Clinical Relevance:** This treatment has not been studied in the unique environment encountered by Paramedics in the Pre-Hospital setting. If this treatment is found to be effective, it may offer a very simple, extremely inexpensive and non-invasive (basic life support) approach for the treatment of nausea.

Item 3 Background	

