
Step-by-Step Methods:
 
RECRUITMENT AND RANDOMIZATION PROCESS Patients who report nausea and/or vomiting in the normal evaluation and care of after calling 911 for Emergency Medical Care will be offered enrollment in the study. A short script will be attached to the outside of each study packet providing information about the study. Verbal (waiver of documentation informed consent will be requested) permission will be obtained to start randomization. If the patient agrees to enroll then the study packet will be opened and utilized.
 
PROCEDURES AND LOGISTICS All Advanced Life Support Ambulances in the San Antonio Fire Department will have sealed numbered opaque boxes or envelopes with either:
 
 
• Three large 2 ply 70% Isopropyl Alcohol swabs
 
 
OR
 
 
• Ondansetron (Zofran) 4mg for IV/IM use (standard of care)
 
 
These study packets will have similar weight, shape and contour despite the contents. If needed, props may be included to make packages similar in weight, contour or sound when shaken so as to not reveal its true contents. The goal is to enroll at least 400 patients over a 1 year period.
 
For each arm, the package will contain a step by step instruction checklist. Six Visual Nausea Severity Scoring cards will be provided with a marking pen to record timed nausea levels before and upon arrival to the Emergency Department and 15 minutes after treatment whichever comes first. The treatment protocol for each arm will be:
 
70% Isopropyl Alcohol
 
 
1. Mark Time and Visual Nausea Severity Score 0-10
 
2. Remove alcohol prep with gloved hand
 
3. Place under nares of the patient
 
	
--	--

4. Instruct the patient to take three separate deep inhalations of the Isopropyl vapors through their nose
5. Record time of treatment on back of first Visual Nausea Severity Score card.
6. Mark time and Subsequent Visual Nausea Severity Scores upon arrival to the Emergency Department at indicated time intervals.
7. If patient still has significant nausea and or vomiting after ten minutes provide rescue Ondansetron therapy with 4mg of Ondansetron slow IV push or IM
8. Mark time and Visual Nausea Severity Score upon arrival to the Emergency Department on third card.
9. Document all interventions on electronic Patient Care record as per usual procedures.

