10. Complete Paramedic evaluation tool.
11. Envelope or box, with Consent, score cards and Paramedic evaluation tool will be returned to Medic Officer on duty and a new study packet will be replaced.
12. Used Study Packets will be collected by the Investigators

Ondansetron 4mg IV/IM (standard of care)

1. Mark Time and Visual Nausea Severity Score 0-10 on first enclosed card.
2. Start IV if not already done so.
3. If unable to obtain IV access in two attempts use intramuscular route.
4. Inject 4mg of Ondansetron slow IV push or IM.
5. Record time of treatment on back of first Visual Nausea Severity Score card.
6. Mark time and Second Visual Nausea Severity Score upon arrival to the Emergency Department or 10 minutes after treatment whichever comes first.
7. If patient still has significant nausea and or vomiting after ten minutes provide rescue an additional dose of Ondansetron therapy with 4mg of Ondansetron slow IV push or IM
8. Mark time and Visual Nausea Severity Score upon arrival to the Emergency Department on third card.
9. Document all interventions on electronic Patient Care record as per usual procedures.
10. Complete Paramedic evaluation tool.
11. Envelope or box, with Consent, score cards and Paramedic evaluation tool will be returned to Medic Officer on duty and a new study packet will be replaced.
12. Used Study Packets will be collected by the Investigators.

Data Analysis Plan: A secure excel spreadsheet tool will be used to abstract data from the research data collection documents and the EMS electronic patient care record. The patient will only be identified by the randomization number, incident number, age (if greater than 89 age will be indicated by <89 years), sex and date of service in the database and on all study packet materials. All relevant time intervals and Visual Nausea Severity Scores will be recorded for enrolled patients. Time to treatment will be compared between the two arms of the study as well as changes in Visual Nausea Severity Scores. Treatment failures requiring additional Ondansetron will be characterized. Paramedic will be asked to evaluate the treatment provided for ease of use, time needed to complete the treatment and their impression of effectiveness of the assigned treatment. T-test and confidence intervals will be utilized to determine statistical significance.

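### The first post-treatment nausea score has conflicting or missing times (10 minutes, 15 minutes, none stated) and no analysed score is named, so the arms can be compared at different elapsed times

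*Combined protocol and SAP*

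**What the plan says.** Four places in the combined protocol and SAP time the score that follows treatment.

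- Item 2 (Abstract, Methods) and Item 6 (Procedures and Logistics), covering both arms: "upon arrival to the Emergency Department and 15 minutes after treatment whichever comes first".
- Item 6, ondansetron checklist, step 6: "Mark time and Second Visual Nausea Severity Score upon arrival to the Emergency Department or 10 minutes after treatment whichever comes first".
- Item 6, isopropyl alcohol checklist, step 6: "Mark time and Subsequent Visual Nausea Severity Scores upon arrival to the Emergency Department at indicated time intervals". The documents list no intervals to which this could refer.

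The steps that follow are parallel. Step 7 opens rescue at the same point in both arms: "If patient still has significant nausea and or vomiting after ten minutes provide rescue Ondansetron therapy" for isopropyl alcohol and "If patient still has significant nausea and or vomiting after ten minutes provide rescue an additional dose of Ondansetron" for ondansetron. Step 8 is worded identically: "Mark time and Visual Nausea Severity Score upon arrival to the Emergency Department on third card".

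The Data Analysis Plan in Item 6 compares time to treatment and score changes between arms, using a t-test and confidence intervals. It does not say which card or time supplies the change. It does say that time intervals are recorded and that treatment failures needing more ondansetron are described. The abstract calls the trial an equivalence study of nausea reduction after treatment, also without a time point.

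**The concern.** Paramedics will work from the checklists, so step 6 in practice defines the outcome. As printed, it fixes a time in one arm and leaves it open in the other, and the fixed time disagrees with the text that governs both arms. The analysis section does not repair this, because it names no score.

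Two things could then enter the between-arm difference besides treatment. One is elapsed time: nausea may settle by itself, or get worse during transport, which the Background says often provokes motion sickness. The other is rescue. A score taken after rescue in the isopropyl alcohol arm would include an effect of the comparator drug, and in an equivalence study that could hide a real shortfall. A score not taken at the intended time cannot be recovered afterwards.

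**Working it through.** **Text comparison.** The stated times are 10 minutes or arrival (ondansetron checklist), 15 minutes or arrival (common text, reading its joining word with the first-to-occur clause) and no number (isopropyl alcohol checklist). The first two contradict each other; the third is undefined. It has three possible readings:

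1. The common rule, 15 minutes or arrival.
2. Serial scores at intervals printed elsewhere. The plural and the supply of cards ("Six Visual Nausea Severity Scoring cards will be provided with a marking pen") allow this. The arrival score on the third card at step 8 leaves only one card between baseline and arrival, which speaks against it.
3. Arrival only. Step 6 would then duplicate step 8, so this is less likely.

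**Size under reading 1 (illustration).** The documents give no transport time, dosing delay, rate of change in nausea or standard deviation (SD), so every input here is assumed.

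- T, packet opening to ED arrival: gamma, mean 20 min, SD 8 (also 15/6 and 25/8).
- Treatment given at d minutes: 1 for isopropyl alcohol; 6 for ondansetron (also 3 and 9).
- Score due at c minutes after treatment or at arrival, whichever is earlier.

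Mean treatment-to-score time: E[min(max(T − d, 0), c)] = ∫₀ᶜ P(T > u + d) du.

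Central case:

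| Arm | c = 10 | c = 15 |
|---|---|---|
| Isopropyl alcohol | 9.75 | 13.65 |
| Ondansetron | 8.66 | 11.28 |

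- Gap as written: 13.65 − 8.66 = 4.99 min.
- Gap left under one common rule, due only to the assumed later ondansetron dosing: 9.75 − 8.66 = 1.09 min (10-minute rule) or 13.65 − 11.28 = 2.37 min (15-minute rule).
- Part due to the wording: 4.99 − 1.09 = 3.90 min or 4.99 − 2.37 = 2.62 min.

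Over all nine combinations the gap as written is 3.44 to 6.81 min. The wording part is 2.76 to 4.72 min against a 10-minute rule and 0.72 to 4.47 min against a 15-minute rule. The 6.81 and the 0.72 come from mean arrival at 15 min with ondansetron at 9 min, where 15% of ondansetron patients would arrive before dosing. Without that combination the gap ends at 13.65 − 7.47 = 6.18 (20/8, d = 9), and the 15-minute wording part starts at 8.37 − 7.09 = 1.28 (15/6, d = 6).

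**Other readings.** If serial scoring includes a score at 10 minutes or arrival and that score is analysed, the wording part is zero. If isopropyl alcohol is scored only at arrival, the central mean is about 20 − 1 = 19 min, which is 19 − 9.75 = 9.25 min later than under a 10-minute rule.

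**In score points.** With an assumed drift of 0.05 to 0.10 points per minute in either direction, the central wording part is 2.62 × 0.05 = 0.13 to 3.90 × 0.10 = 0.39 points; with no drift it is zero. Taking the goal of 400 patients as 200 per arm and SD 3, the 95% half-width is t(0.975, 398) × 3 × √(2/200) = 0.59 (0.49 to 0.69 for SD 2.5 to 3.5).

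**Rescue.** Scoring is step 6 and rescue is step 7 in both checklists, so the sequence puts the score first. The clock agrees with that for a score due by 10 minutes. It does not for a score due at 15 minutes or at a later arrival, since rescue is already open after ten minutes.

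**The case against.** The strongest reply is that this is a drafting slip. The two checklists are otherwise parallel, with a baseline card, one score at step 6, rescue at step 7 and arrival on the third card. The missing intervals may be printed on cards that the documents do not show. Arrival scores are worded alike in both arms, times are marked and failures are described, so naming the analysed score would settle much of the problem. The illustrated shift is also smaller than the confidence interval half-width.

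Much of this stands. It rules out inferring that the arms will certainly be scored at different times, or that the result is biased towards equivalence: the text proves a contradiction and a gap, and fixes neither size nor direction. A reader might also infer that a quotable share of isopropyl alcohol scores would follow rescue. The documents give no rescue rate, and the step order points the other way, so no such percentage should be stated.

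What does not stand is that the existing safeguards are enough. The arrival score is not named as the endpoint and can itself follow rescue. Recorded times help only for scores that were taken. A shift from unequal timing is systematic, so a larger sample does not remove it.

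**Conclusion.** The concern holds as a contradiction in the text combined with an unnamed analysed score. The checklists as written can compare the arms at different elapsed times, and a score due after ten minutes sits in conflict with the printed order of scoring and rescue.

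The size is illustrative only: about 3 to 4 minutes between arms in the central case if isopropyl alcohol follows the 15-minute text, and zero if a matching score is taken and analysed. The case for correction rests on the wording and not on these figures. The documents do not show which time was intended, nor whether the second-card or the arrival score was meant for analysis. A reader might take the second card as the intended primary score, but nothing ranks it above arrival.

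**What to change.** Before packets are printed:

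1. Reconcile the abstract, the procedures text and both checklists to one scoring time, worded identically in step 6 of each. If intervals are intended, print them in the step.
2. In the Data Analysis Plan, name one analysed score, the same in both arms. It may be the second-card or the arrival score; that is the sponsor's choice.
3. State whether that score is recorded before any rescue given under the existing rule, and how scores taken after rescue are analysed.

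Optionally, use the recorded minutes from treatment to score in a sensitivity analysis, since identical wording reduces but need not remove the timing difference when arrival comes first. The scoring time and the rescue rule stay with the sponsor.

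The cost is a checklist reprint, two aligned sentences and a few sentences in the analysis plan. Sample size and treatment do not change.

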
Describe past experimental and/or clinical findings leading to the formulation of your study.
 
For research involving unapproved drugs, describe animal and human studies.
 
For research that involves approved drugs or devices, describe the FDA approved uses of this drug/device in relation to your protocol.
	
Nausea is a common symptom encountered in the Emergency Medical Services (EMS) environment that is often treated with oral or intravenous anti-emetic medications. Post-operative patients with modern anesthesia techniques and processes still have a 20-30% incidence of Nausea and/or vomiting. Nausea is a complicated symptom that is tough to arise from the vomiting center in the lateral reticular formation in the brainstem. Afferent inputs from the cerebellum, higher cortical centers, the vestibular apparatus, the glossopharyngeal nerve and the vagal nerve inputs contribute to the process of the perception of nausea. Chemoreceptors in the Chemoreceptor Trigger Zone (CTZ) are located on the brain surface and are highly vascularized leading to increased exposure to neurotransmitters such as Serotonin (5-HT-3), histamine (H1) acetylcholine and dopamine. Blocking such neurotransmitter stimulation with targeted medications such as antihistamines or 5-HT-3 antagonists such as Ondansetron.
 
Nausea is a common symptom encountered in the Emergency Medical Services (EMS) environment that is often treated with oral or intravenous anti-emetic medications. Many patients do not respond well to this therapy, and EMS services that have only basic life support (BLS) capabilities may not have any good treatment currently. Additionally, because of the configuration of modern day ambulances, the patient is transported in a rear facing position in the patient compartment with very limited view of the environment. This method of transport frequently causes motion sickness.
 
Motion sickness is thought to be caused by inadequate adaptation of the body to conflicts between vestibular, visual, other proprioceptive inputs and inhibition of the vestibular cerebellum. Common therapies may include antihistamines, benzodiazepines, tricyclic antidepressants and/or scopolamine. 3 Sakata

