Item 4 Purpose and rationale Insert purpose, objectives and research questions/hypotheses here. If you cut and paste from another document, make sure the excerpted material answers the question	Insert purpose: IPA Therapy may offer a very inexpensive, easy to administer, and effective alternative to medication therapy for nausea and vomiting in the prehospital

Item 5 Study Population(s) Being Recruited  In your recruitment plan, how many different populations of prospective subjects do you plan to target? Provide number: 1	Identify the criteria for inclusion :	Identify the criteria for exclusion :
--	--	--

e.g., a population can be individuals with type 2 diabetes controlled with diet and/or a population of healthy controls. Or a population can be individuals attending an education program, etc.
 
List each different population on a separate row and provide a short descriptive label: (e.g., normal-healthy, diabetics, parents, children, etc.)
 
To add rows use copy & paste
		

EMS patients complaining of nausea
	
Adults (non-pregnant) age 18 years or older with a symptom of nausea and/or vomiting requiring treatment by EMS
	
 
• Children not yet 18 years of Age
 
• Prisoners or those under arrest
 
• Patients known or suspected to be Pregnant
 
• Clinical Intoxication
 
• Patients unable to provide informed consent
 
• Recent Upper respiratory Tract infection
 
• Inability to follow instructions
 
• Inability to inhale through Nares
 

#### Item 6

**Research Plan / Description of the Research Methods a.** *Provide a comprehensive narrative describing the research methods. Provide the plan for data analysis (include as applicable the sample size calculation).*

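### Post-treatment score timing differs between the two checklists and the narrative; followed literally, the alcohol checklist needs an ED arrival for its first score, so outcomes can go missing unevenly by arm.

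*Combined protocol and SAP*

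**What the plan says.** Item 5 admits "Adults (non-pregnant) age 18 years or older with a symptom of nausea and/or vomiting requiring treatment by EMS". Neither the inclusion nor the exclusion list mentions transport, and Item 6 has the packet opened once the patient agrees to enrol.

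The timing of scores after treatment is stated in several places:

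- **Narrative (Item 2 abstract and Item 6, before the checklists).** The cards are to "record timed nausea levels before and upon arrival to the Emergency Department and 15 minutes after treatment whichever comes first". In Item 6 this sits beside the sentence "For each arm, the package will contain a step by step instruction checklist", so it covers both arms.
- **Alcohol checklist, step 6.** "Mark time and Subsequent Visual Nausea Severity Scores upon arrival to the Emergency Department at indicated time intervals". No intervals are given in the checklist.
- **Ondansetron checklist, step 6.** "Mark time and Second Visual Nausea Severity Score upon arrival to the Emergency Department or 10 minutes after treatment whichever comes first".
- **Step 8, same wording in both checklists.** "Mark time and Visual Nausea Severity Score upon arrival to the Emergency Department on third card".

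Between these, alcohol step 7 has a symptom check tied to rescue: "If patient still has significant nausea and or vomiting after ten minutes provide rescue Ondansetron therapy". It asks for no score. The Data Analysis Plan compares changes in the nausea score between arms by t-test and confidence intervals. It names no time point and has no rule for a patient without a score.

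**The concern.** The paramedic works from the checklist in the packet. In the alcohol checklist, both score steps after treatment are worded to ED arrival. In the ondansetron checklist, one of the two can be met by elapsed time alone. Since transport is not a condition of entry, a patient could be randomised and treated and then not taken to an ED. That patient could have a baseline score and nothing else in the alcohol arm, but a usable change score in the ondansetron arm.

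Transport is decided after randomisation and could be related to response or to treatment. If so, a comparison of patients with scores would no longer be a comparison of the randomised groups. That matters in a trial described as an equivalence study, where the conclusion rests on a small between-arm difference. Even when every patient is transported, the different rules can place the two arms' scores at different times after treatment.

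**Working it through.** There is no stated figure to reproduce. The enrolment goal of at least 400 comes without SD, margin, power or allocation ratio. The check is therefore a comparison of the texts, followed by an illustration.

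**1. Timing rules side by side**

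| Source | Score after treatment | Needs an ED arrival? |
|---|---|---|
| Narrative, both arms (Items 2 and 6) | ED arrival or 15 min, the earlier | No |
| Alcohol step 6 | ED arrival, at unlisted intervals | Yes, as worded |
| Ondansetron step 6 | ED arrival or 10 min, the earlier | No |
| Step 8, both arms | ED arrival | Yes |

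**2. Transported patient.** Let T be minutes from treatment to ED arrival. Ondansetron step 6 falls at min(10, T), the narrative score at min(15, T), and alcohol step 6, read literally, at T. For T of 10 or less all three agree. For an assumed T = 20 they fall at 10, 15 and 20 minutes. The alcohol score, and a 15-minute score, would then come after the ten-minute rescue check.

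**3. Patient not transported.** Let C be minutes of EMS contact after treatment.

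- Ondansetron checklist: scored at step 6 if C is at least 10.
- Alcohol checklist, literal: no score at any C.
- Narrative rule: scored in either arm if C is at least 15.
- Step 8: lost in both arms.

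**4. Illustration of size.** Let q be the share of the alcohol arm left unscored for this reason, and d the extra mean improvement of those patients over the scored ones. Assume no matching loss in the ondansetron arm. The full-arm mean improvement is m = (1 − q)·m_obs + q·m_miss, so m_obs − m = −q·d. A positive d understates alcohol and a negative d overstates it.

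With an assumed 1:1 split (200 per arm) and an assumed change SD of 2.5 points, SE = 2.5 × √(2/200) = 0.25 points. With the unscored patients removed, SE is multiplied by √{[1/(200(1 − q)) + 1/200] / (2/200)}.

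| q (assumed) | Alcohol patients scored | Rise in SE | d (assumed) | Size of bias, q·d | Bias / 0.25 |
|---|---|---|---|---|---|
| 0 (15-minute rule followed) | 200 | 0% | any | 0 | 0 |
| 5% | 190 | 1.3% | 1 | 0.05 | 0.2 |
| 10% | 180 | 2.7% | 2 | 0.20 | 0.8 |
| 15% | 170 | 4.3% | 3 | 0.45 | 1.8 |

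The loss of precision is small. Any harm would come from bias, which further enrolment does not reduce.

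**The case against.** A reader might infer that every non-transported alcohol patient has no outcome score, and that the arms therefore drop out unevenly to alcohol's disadvantage. The documents do not support that.

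- **The narrative rule.** It applies to both arms and supplies a 15-minute score without an ED arrival.
- **Alcohol step 6 may be garbled timed scoring.** It asks for scores in the plural, precedes the ten-minute check, and would merely duplicate step 8 if it meant ED arrival alone. Six cards are supplied, which also suggests serial scoring.
- **The endpoint is not named.** If the change is taken to step 8, a non-transported patient loses it in either arm. The uneven loss requires the second score to be the endpoint, the literal checklist to prevail, and the ondansetron patient to stay in contact for 10 minutes.
- **Non-transport is not described.** The background treats transport as the usual setting ("the patient is transported in a rear facing position in the patient compartment"). Nothing in the documents says that responders decline transport, or do so more often after alcohol.

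All of this stands, and it makes the missing-outcome problem conditional. It does not remove the inconsistency. The 15-minute alternative appears in neither checklist, the ondansetron checklist uses a different time, the step 7 check produces no score, and the analysis plan does not say which score counts.

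**Conclusion.** The point holds as an inconsistency in score timing that can produce arm-dependent missing outcomes. What the documents establish is that three different rules govern the first post-treatment score, that only the alcohol version, as worded, depends on ED arrival, that transport is not required for entry, and that the analysis names no time point or missing-score rule.

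The consequence is possible but not shown. Its size and direction are unknown. It is nil if the narrative's 15-minute rule is followed and patients remain in contact that long. The upper figure of 0.45 points (1.8 standard errors) pairs the two most extreme assumed values and should not be read as an estimate. The non-transport share, its link to response, the SD and the allocation ratio are all assumptions. The change is worth making because it costs almost nothing and removes a source of bias that the analysis could not repair later.

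**What to change.** Reconcile the Item 2 abstract, the Item 6 narrative and step 6 of both checklists to one elapsed-time post-treatment score:

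- Use the same wording in both checklists.
- Take the score at the chosen time after treatment whether or not the patient is transported, or at the end of EMS contact if that comes first.
- Record it before any step 7 rescue. This concerns only when the score is taken; the rescue rule is not at issue here.

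In the Data Analysis Plan, name the change from baseline to that score as the arm comparison. Keep all randomised patients in it, transported or not, and state how a missing score is handled. Do not restrict the comparison to transported patients. Add a transported yes/no item to the returned packet, and report non-transport and missing scores by arm. Keep the step 8 score as secondary: it follows the rescue step and comes at variable times, so it should not carry the comparison.

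The cost is a wording change in the narrative and two checklist steps, one tick box and a few sentences of analysis plan. No extra patients, staff or procedures are needed. The small downside is that patients whose EMS contact ends early are scored at slightly variable times.

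### Nausea scores taken after rescue ondansetron can enter the equivalence comparison, and would understate an alcohol deficit if alcohol is the weaker treatment

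*Combined protocol and SAP*

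**What the plan says.** The Item 2 abstract sets the aim: "This will be a randomized equivalence study comparing the reduction in a patient's reported level of nausea after treatment". It gives the clinical motive as follows: if alcohol works, "it may offer a very simple, extremely inexpensive and non-invasive (basic life support) approach for the treatment of nausea".

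Item 6 sets out two checklists.

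- **Rescue, alcohol arm (step 7):** "If patient still has significant nausea and or vomiting after ten minutes provide rescue Ondansetron therapy with 4mg of Ondansetron".
- **Rescue, ondansetron arm (step 7):** on the same ten-minute criterion, "provide rescue an additional dose of Ondansetron therapy with 4mg of Ondansetron slow IV push or IM".
- **Score after the rescue step (step 8, both arms):** "Mark time and Visual Nausea Severity Score upon arrival to the Emergency Department on third card".
- **Score before the rescue step, ondansetron arm (step 6):** "Mark time and Second Visual Nausea Severity Score upon arrival to the Emergency Department or 10 minutes after treatment whichever comes first".
- **Score before the rescue step, alcohol arm (step 6):** further scores, in the plural, tied both to ED arrival and to intervals that the step does not state.

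The Item 2 and Item 6 narratives give another timing: "upon arrival to the Emergency Department and 15 minutes after treatment whichever comes first".

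On analysis, Item 6 says "Time to treatment will be compared between the two arms of the study as well as changes in Visual Nausea Severity Scores", using a t-test and confidence intervals. Patients who need additional ondansetron are to be described. The plan names no primary score or time point and gives no rule for a score taken after rescue.

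**The concern.** Rescue in the alcohol arm is the drug that alcohol is being compared with. Once a rescued alcohol patient is scored again, that score reflects alcohol plus ondansetron. If such scores enter the by-arm comparison, then the worse alcohol performs, the more of its arm receives ondansetron, and the better its later scores look. In a superiority trial this dilution would count against the claim. In an equivalence trial it can count in favour.

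The stated use is also affected. The Item 3 background says that basic-life-support crews have no current options, and alcohol is proposed to fill that gap. A result that partly reflects later ondansetron would not tell those crews what alcohol achieves alone.

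Part of the loss could be permanent. If a rescued alcohol patient has no score taken before rescue, no analysis can supply one.

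**Working it through.** **Which scores can follow rescue.** Rescue is due from ten minutes.

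- ED arrival (step 8): after rescue if the patient arrives later than ten minutes and was rescued; otherwise before.
- Narrative score (15 minutes or ED arrival, whichever is first): before rescue is due if arrival is within ten minutes. Otherwise at most 15 − 10 = 5 minutes after rescue becomes due.
- Second card, ondansetron arm: at or before ten minutes, so ahead of rescue.
- Second card, alcohol arm: listed before the rescue step, but with no clear time.

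**Figures in the documents.** The only design figure is the goal of at least 400 patients. No margin, SD, alpha or power is given, so it cannot be reproduced. There are no rescue rates or rescue effects either. Everything below is assumption.

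**Arithmetic.** Let D be the deficit of alcohol without rescue, r the share rescued and e the extra score reduction from rescue (A alcohol, O ondansetron):

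observed difference = D − (rA·eA − rO·eO)

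With D = 1.0:

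| Rescue rates A / O | e = 1 in both | e = 2 in both | larger effect in alcohol arm |
|---|---|---|---|
| 30% / 20% | 1.0 − (0.30 − 0.20) = 0.90 | 1.0 − (0.60 − 0.40) = 0.80 | 2 v 1: 1.0 − (0.60 − 0.20) = 0.60 |
| 40% / 25% | 1.0 − (0.40 − 0.25) = 0.85 | 1.0 − (0.80 − 0.50) = 0.70 | 2 v 1: 1.0 − (0.80 − 0.25) = 0.45 |
| 50% / 25% | 1.0 − (0.50 − 0.25) = 0.75 | 1.0 − (1.00 − 0.50) = 0.50 | 2.5 v 1: 1.0 − (1.25 − 0.25) = 0.00 |

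The share hidden is 10–25% with equal 1-point effects, 20–50% with equal 2-point effects, and 40–100% in the last column. If rescue has not acted by the time of the score, e = 0 in both arms and nothing is hidden.

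**Simulation with rescue driven by the score.** Assumptions: ten-minute scores limited to 0–10, SD 2.5, ondansetron mean 4 (before limiting), rescue at a score of 5 or more, 200 per arm, margin 1.0, two one-sided tests at 0.025 each. Positive differences mean alcohol is worse. Brackets give the chance of declaring equivalence.

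| Difference without rescue | Rescued A / O | e = 1 / 1 | e = 2 / 2 | e = 2 / 1 |
|---|---|---|---|---|
| 0.95 (4%) | 50% / 34% | 0.79 (18%) | 0.64 (57%) | 0.30 (97%) |
| 1.43 (0%) | 58% / 34% | 1.19 (0.2%) | 0.95 (5%) | 0.61 (55%) |
| 0 (98%) | about 34% / 34% | 0 | 0 | −0.35 (94%) |
| −0.91 (6%) | 21% / 34% | −0.78 (20%) | −0.65 (54%) | −0.99 (3%) |

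In the first row about 17%, 33% and 68% of the deficit is hidden: (0.95 − 0.79)/0.95, (0.95 − 0.64)/0.95 and (0.95 − 0.30)/0.95. A deficit of 0.95 lies just inside the assumed margin, so the second row is the true false-equivalence case. Both rows with alcohol weaker move toward equivalence. The last two rows show no shift, a shift toward zero, or a shift in favour of alcohol, depending on the effects.

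**The case against.** The strongest reply is that the plan never says post-rescue scores will be used. It names no time point, and the authors may have meant the second-card score. That is fair. What is documented is a missing restriction, so the claim is that such scores can enter, not that they will.

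Three further replies hold.

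- The alcohol checklist does call for scores before its rescue step, and the numbering of the third card implies a second one. The interval may be printed on packet material that is not shown. A reader might infer that no pre-rescue score is taken in the alcohol arm. The documents support only that its time is not clearly stated.
- A reader might infer that every later score follows rescue. The narrative takes the earlier of ED arrival and 15 minutes, which rules that out for early arrivals, and it leaves at most five minutes for rescue to act on the 15-minute score. The concern weighs most on a late ED-arrival score.
- Only patients who meet the criterion cross over, and the second dose in the ondansetron arm is a partial offset.

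Score times and interventions are recorded, so an analysis rule alone can separate scores wherever a pre-rescue score exists. It cannot help where none was taken.

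Finally, alcohol first with rescue against ondansetron first with rescue is a legitimate strategy question for the advanced-life-support ambulances in this trial. It is not the question for crews without ondansetron, so it can stand beside the primary comparison but not replace it.

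**Conclusion.** The gap is real: the primary score is unspecified, rescued patients have no analysis rule, and the two arms do not share a clear pre-rescue assessment. Followed as written, the plan allows ondansetron's effect into the alcohol arm's result.

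The direction is conditional. A reader might infer that the bias always runs toward equivalence. It does so when alcohol is the weaker treatment, is therefore rescued more often, and rescue acts before the score. That is the case in which a false claim matters. The background section expects alcohol to be as effective with faster onset. If that is so, the shift may be nil or may favour alcohol.

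The size is unknown. A reader might take 40–100% hidden as the estimate, but that range needs rescue to work 2 to 2.5 times as well in the alcohol arm. Equal effects at the same rates give 10–50%, and zero is possible. Confidence is high on the missing rule and low on any single figure.

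**What to change.** Leave the rescue rule as it is.

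1. Reconcile step 6 across the two checklists and with the narrative, so that both arms take the second-card score at the same time: 10 minutes after treatment or ED arrival, whichever comes first, and before any rescue dose.
2. State in the Data Analysis Plan that the primary equivalence comparison is the change from baseline to that score, in all patients and both arms.
3. Report post-rescue and ED-arrival scores separately, as results of the treatment sequence.
4. Add a sensitivity analysis that counts rescued patients as having no improvement.

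A common time is preferable to the last score before rescue. The latter would mix assessments at about ten minutes in rescued patients with assessments at up to 15 minutes in others.

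The cost is one reworded checklist step and a few sentences of analysis plan; the six cards already in the packet suffice. The change must precede enrolment, because a score not taken cannot be recovered. The price is that the ED-arrival comparison no longer supports the equivalence claim, and the primary result covers only the first ten minutes.
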